### **7.5.7. On-Treatment Hepatitis C Management**

If a subject tests positive for HCV RNA at screening or develops signs or symptoms of active Hepatitis C virus Gilead recommends that local medical practice is followed at the discretion of the Investigator. Investigational medicinal product may be continued without dose interruption. Should the Investigator decide to initiate Hepatitis C treatment the Investigator must contact the Gilead Medical Monitor to confirm that no drug-drug interactions are expected. Subjects should return to the clinic for scheduled or unscheduled follow up visit(s) according to local medical practice for laboratory evaluations. If Hepatitis C treatment is initiated, Investigators should use the Gilead provided retest laboratory kits to manage the active Hepatitis C.

### **7.5.8. Management of Potential Nephrotoxicity**

Estimated glomerular filtration rate according to the Cockcroft-Gault formula (eGFRC-G), will be followed post-baseline during the study. All subjects with estimated GFR < 50 mL/min (0.83 mL/sec) must have serum creatinine and subject's weight measured again within 3 calendar days of receipt of results.

If a subject has confirmed eGFRC-G < 50 mL/min, the Gilead Medical Monitor should be notified and discontinuation of the study drug should be discussed. For subjects with confirmed eGFRC-G < 50 mL/min who are not discontinued based on toxicity management procedures above and are considered to have stable renal function per Principal Investigator and Gilead Medical Monitor, it is not mandatory to repeat eGFR assessments within 3 days.

## **7.6. Special Situations Reports**

### **7.6.1. Definitions of Special Situations**

Special situation reports include all reports of medication error, abuse, misuse, overdose, reports of adverse events associated with product complaints, reports of adverse reactions in infants following exposure from breastfeeding, occupational exposure with an adverse event, and pregnancy reports regardless of an associated AE.

Medication error is any unintentional error in the prescribing, dispensing, or administration of a medicinal product while in the control of the health care provider, subject, or consumer.

Abuse is defined as persistent or sporadic intentional excessive use of a medicinal product by a subject.

Misuse is defined as any intentional and inappropriate use of a medicinal product that is not in accordance with the protocol instructions or the local prescribing information.

An overdose is defined as an accidental or intentional administration of a quantity of a medicinal product given per administration or cumulatively which is above the maximum recommended dose as per protocol or in the product labelling (as it applies to the daily dose of the subject in question). In cases of a discrepancy in drug accountability, overdose will be established only

when it is clear that the subject has taken the excess dose(s). Overdose cannot be established when the subject cannot account for the discrepancy except in cases in which the investigator has reason to suspect that the subject has taken the additional dose(s).

Product complaint is defined as complaints arising from potential deviations in the manufacture, packaging, or distribution of the medicinal product.

Occupational exposure with an AE is defined as exposure to a medicinal product as a result of one's professional or non-professional occupation.

## **7.6.2. Instructions for Reporting Special Situations**

### **7.6.2.1. Instructions for Reporting Pregnancies**

The investigator should report pregnancies in study subjects that are identified after initiation of study medication and throughout the study, including the post-study drug follow-up period, to the Gilead DSPH using the pregnancy report form within 24 hours of becoming aware of the pregnancy.

Refer to the instructions below and the eCRF completion guidelines for full instructions on the mechanism of pregnancy reporting.

The pregnancy itself is not considered an AE nor is an induced elective abortion to terminate a pregnancy without medical reasons.

Any premature termination of pregnancy (eg, a spontaneous abortion, an induced therapeutic abortion due to complications or other medical reasons) must be reported within 24 hours as an SAE. The underlying medical reason for this procedure should be recorded as the AE or SAE term, as applicable.

A spontaneous abortion is always considered to be an SAE and will be reported as described in Section 7.3.2. Furthermore, any SAE occurring as an adverse pregnancy outcome post study must be reported to Gilead DSPH.

The subject should receive appropriate monitoring and care until the conclusion of the pregnancy. The outcome should be reported to Gilead DSPH using the pregnancy outcome report form. If the end of the pregnancy occurs after the study has been completed, the outcome should be reported directly to Gilead DSPH. Gilead DSPH contact information is as follows:

Email: Safety\[contact] and [contact].

Refer to [Appendix 6](#) for Pregnancy Precautions, Definition for Female of Childbearing Potential, and Contraceptive Requirements.

#### 7.6.2.2. Reporting Other Special Situations

All other special situation reports must be reported on the special situations report form and forwarded to Gilead DSPH within 24 hours of the investigator becoming aware of the situation. These reports must consist of situations that involve study IMP and/or Gilead concomitant medications, but do not apply to non-Gilead concomitant medications.

Special situations involving non-Gilead concomitant medications does not need to be reported on the special situations report form; however, for special situations that result in AEs due to a non-Gilead concomitant medication, the AE should be reported on the AE form.

Any inappropriate use of concomitant medications prohibited by this protocol should not be reported as “misuse,” but may be more appropriately documented as a protocol deviation.

Refer to Section [7.6](#) and the eCRF completion guidelines for full instructions on the mechanism of special situations reporting.

All clinical sequelae in relation to these special situation reports will be reported as AEs or SAEs at the same time using the AE eCRF and/or the SAE report form. Details of the symptoms and signs, clinical management, and outcome will be reported, when available.

## **8. STATISTICAL CONSIDERATIONS**

### **8.1. Analysis Objectives and Endpoints**

#### **8.1.1. Analysis Objectives**

The primary objective of this study is to evaluate the efficacy of switching to a GS-9883/F/TAF FDC versus staying on baseline regimen (SBR) in virologically suppressed HIV-1 infected women as determined by the proportion of subjects with HIV-1 RNA  $\geq$  50 copies/mL at Week 48.

The secondary objective of this study is to evaluate the safety, and tolerability of the two treatment groups through Week 48.

#### **8.1.2. Primary Endpoint**

The primary efficacy endpoint is the proportion of subjects with HIV-1 RNA  $\geq$  50 copies/mL at Week 48 as determined by the FDA-defined snapshot algorithm.

#### **8.1.3. Secondary Endpoint**

Secondary endpoints include:

- The proportion of subjects with HIV-1 RNA  $<$  50 copies/mL at Week 48 as determined by the US FDA-defined snapshot algorithm
- The change from baseline in CD4+ cell count at Week 48

### **8.2. Analysis Conventions**

#### **8.2.1. Analysis Sets**

##### **8.2.1.1. All Randomized**

The randomized analysis set includes all subjects who are randomized into the study. This is the primary analysis set for by-subject listings.

##### **8.2.1.2. Efficacy**

##### **8.2.1.2.1. Full Analysis Set (FAS)**

The primary analysis set for efficacy analyses is defined as full analysis set (FAS), which will include all subjects who (1) are randomized into the study (2) have received at least 1 dose of study drug. Subjects will be grouped according to the treatment to which they were randomized.

##### **8.2.1.2.2. Per-Protocol (PP) Analysis Set**

The secondary analysis set for efficacy analyses is defined as per-protocol (PP) analysis set, which will include all subjects who (1) are randomized into the study, (2) have received at least 1 dose of study drug (3) have not committed any major protocol violation, including the violation of key entry criteria. Subjects will be grouped according to the treatment they actually received.

Subjects meeting any of the following criteria will be excluded from the Week 48 PP analysis set:

- Subjects who do not have an on-treatment HIV-1 RNA laboratory test in the Week 48 analysis window, except when missing is due to discontinuation of study drug for lack of efficacy.
- Subjects who meet the exclusion criterion for receiving ongoing therapy with any of the medications listed in the table in protocol Section 5 including drugs not to be used with GS-9883, FTC, TAF, EVG, COBI, ATV and RTV.
- Non adherence to study drug: subjects with adherence rate for active study drug up to the Week 48 Visit below the 2.5th percentile.

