## **6.13. Virologic Failure**

Virologic failure is defined as virologic rebound or having HIV-1 RNA  $\geq 50$  copies/mL at study drug discontinuation or Week 48.

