#### **8.5.1.1. US FDA-defined Snapshot Algorithm**

The analysis window at Week 48 is defined as from Study Day 295 to Study Day 378, inclusive. All HIV-1 RNA data collected on-treatment (ie, including data collected up to 1 day after the last dose date of study drug) will be used in the snapshot algorithm. Virologic outcome will be defined as the following categories:

- **HIV-1 RNA < 50 copies/mL:** this includes subjects who have the last available on-treatment HIV-1 RNA < 50 copies/mL in the Week 48 analysis window
- **HIV-1 RNA  $\geq 50$  copies/mL:** this include subjects
  - a) Who have the last available on-treatment HIV-1 RNA  $\geq 50$  copies/mL in the Week 48 analysis window, or
  - b) Who do not have on-treatment HIV-1 RNA data in the Week 48 analysis window and
    - 1) Who discontinue study drug prior to or in the Week 48 analysis window due to lack of efficacy, or
    - 2) Who discontinue study drug prior to or in the Week 48 analysis window due to reasons other than lack of efficacy and have the last available on-treatment HIV-1 RNA  $\geq 50$  copies/mL

- **No Virologic Data in the Week 48 Analysis Window:** this includes subjects who do not have on-treatment HIV-1 RNA data in the Week 48 analysis window because of the following:
  - a) Discontinuation of study drug prior to or in the Week 48 analysis window due to reasons other than lack of efficacy and the last available on-treatment HIV-1 RNA is < 50 copies/mL or,
  - b) Missing data during the window but on study drug

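### The Week 48 per-protocol rule removes some women whom the snapshot counts as failures, depending on the recorded reason for stopping

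*Protocol*

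**What the plan says.** Protocol section 8.5.1.1 sets the Week 48 window "from Study Day 295 to Study Day 378, inclusive" and uses on-treatment RNA only, "including data collected up to 1 day after the last dose date of study drug". A woman with no such result in the window is still classed as HIV-1 RNA ≥ 50 copies/mL by either of two routes:

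- b)1): she stopped study drug for lack of efficacy.
- b)2): she belongs to those "Who discontinue study drug prior to or in the Week 48 analysis window due to reasons other than lack of efficacy" and her last on-treatment RNA was 50 or more.

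Protocol section 8.2.1.2.2 excludes from the Week 48 PP set women with no on-treatment RNA result in that window, "except when missing is due to discontinuation of study drug for lack of efficacy". That is the only exception. The same section gives the set its role: "The secondary analysis set for efficacy analyses is defined as per-protocol (PP) analysis set".

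Protocol section 6.13 is broader on failure: "Virologic failure is defined as virologic rebound or having HIV-1 RNA" of 50 copies/mL or more at study drug discontinuation or Week 48, whatever the reason for stopping.

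The primary analysis uses the FAS (section 8.5.1). The supplied SAP covers only the final all-B/F/TAF analysis (SAP section 2.3). It defines no PP set (SAP section 3.1) and does not change the rule.

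**The concern.** A PP set normally leaves out women who provide no information on the endpoint. Those in the snapshot's no-virologic-data category fit that description. The b)2) women do not: the algorithm has already classed them as events. The PP rule keeps b)1) events and removes b)2) events, and what separates the two is the stopping reason on the form.

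The trial is open label, and protocol section 6.7 lists lack of efficacy, toxicity, subject request and noncompliance as separate grounds for stopping. A woman with rebound could plausibly be recorded under more than one of them. Her presence in PP as a failure then turns on a label assigned by someone who knows her treatment.

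In a non-inferiority trial a reader will compare PP with FAS to judge robustness. With about 4.7 failures expected per arm (2% of 235), one woman moves the difference by about 0.43 points (1/235), so a few exclusions tied to outcome can make that comparison misleading.

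**Working it through.** **Inputs from the documents.** 235 women per arm, 2% failures assumed in both arms, a 4-point margin and one-sided 0.025 (protocol section 8.8); a two-sided 95% interval by an exact method that is not named (section 8.5.1.2).

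**The plan's own figure.** The standard error is √(2 × 0.02 × 0.98 / 235) = 0.01292. Power is Φ(0.04/0.01292 − 1.96) = 87.2%, which matches the stated figure of at least 87%.

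**Which snapshot classes survive the PP rule** (women with no on-treatment RNA in the window):

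| Snapshot class | Event? | Kept in PP? |
|---|---|---|
| b)1) stopped for lack of efficacy | yes | yes |
| b)2) stopped for another reason, last RNA ≥ 50 | yes | no |
| No virologic data | no | no |

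**Assumptions.** The documents give neither b)2) counts nor a dropout rate. I take 12 women per arm (about 5%) with no virologic data, so PP has 235 − 12 = 223 per arm if all failures are kept, and I vary the b)2) count. Two rows use a round 220 per arm instead.

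**Method.** The upper bound is the Miettinen-Nurminen score limit: the δ at which (p̂₁ − p̂₀ − δ)/√v(δ) = −1.96. Here v(δ) is the variance at the maximum-likelihood rates constrained to differ by δ, multiplied by N/(N−1), where N is the two arms combined. Group 1 is GS-9883/F/TAF and group 0 is SBR.

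| Failures (switch v SBR) and b)2) removed | PP with all failures kept | PP as written |
|---|---|---|
| 5 v 5, one per arm | 5/223 v 5/223: 3.18% | 4/222 v 4/222: 2.96% |
| 5 v 5, two per arm | 3.18% | 3/221 v 3/221: 2.72% |
| 5 v 5, three per arm | 3.18% | 2/220 v 2/220: 2.44% |
| 8 v 5, three from switch arm | 8/223 v 5/223: 4.96% | 5/220 v 5/223: 3.25% |
| 7 v 5, one from switch arm | 7/220 v 5/220: 4.44% | 6/220 v 5/220: 3.84% |
| 5 v 5, three from SBR | 3.18% | 5/223 v 2/220: 4.35% |
| 6 v 5, one from SBR | 6/220 v 5/220: 3.84% | 6/220 v 4/220: 4.23% |

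In the two rows at 220, taking the removed woman out of the denominator as well gives 3.86% (6/219 v 5/220) and 4.23% (6/220 v 4/219). The full FAS bound is 3.02% for 5 v 5 at 235 per arm and 4.71% for 8 v 5.

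**Error rate when the switch arm is truly 4 points worse (6% v 2%).** Let a share f of failures in each arm be b)2) and a share d = 5% of women have no data. The PP rate as written is p(1 − f)/(1 − pf − d). At f = 20% this gives 0.048/0.938 = 5.12% and 0.016/0.946 = 1.69%, a difference of 3.43 points. By the normal approximation, PP as written then concludes non-inferiority with probability 5.2%. With all failures kept the rates are p/(1 − d), or 6.32% v 2.11%, and the probability is 1.9%. For f = 10%, 30% and 50%, PP as written gives 3.1%, 8.7% and 25.3%.

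**When the direction reverses.** Ignoring denominators, removal takes 6f₁ − 2f₀ points off that true difference. It therefore widens the difference only if the b)2) share of failures in SBR is more than about three times that in the switch arm.

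**The case against.** The strongest reply is that fewer failures overall does not mean a smaller difference. A reader might infer that the rule necessarily favours non-inferiority. The documents do not support that: they give no b)2) counts by arm, and the last two rows of the table show the bound rising. A reader might also infer from 7 v 5 that a single dropped woman would decide the PP result. That is a chosen boundary case. It has a mirror image in SBR and depends on the interval: an exact unconditional interval on the raw difference gives about 10% for both 7 v 5 and 6 v 5 at 235 per arm, so nothing would flip. Both limits stand.

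The consequence is also bounded. The non-inferiority conclusion rests on the FAS, which keeps every b)2) failure, and the protocol attaches no test or decision rule to PP; its use as a robustness check is customary, not stated. This stands too.

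The b)2) class may be small. All entrants have RNA < 50 at screening, stops driven by viraemia may well be coded as lack of efficacy, and section 6.13.1 requires discussion with the Medical Monitor before an investigator stops study drug. These points limit the likely size but do not close the gap: nothing requires such stops to be coded as lack of efficacy.

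Lastly, SAP section 2.2 says the Week 48 analysis was conducted, and the plan that governed it is not among the documents supplied. It may have clarified the exception, which cannot be checked here.

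**Conclusion.** The mismatch between sections 8.2.1.2.2 and 8.5.1.1 is in the text and needs no inference: following both as written removes b)2) endpoint failures from PP according to the recorded stopping reason. PP failure counts are lowered or unchanged. If b)2) failures are removed equally or mainly from the GS-9883/F/TAF arm, the upper bound against the fixed 4% margin falls; if they lie mainly in SBR, it rises. A shift toward non-inferiority is thus an expectation under the first two patterns, not a certainty.

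The size is unknown. The figures are scenarios that rest on assumed b)2) counts, assumed PP sizes and score limits in place of the unnamed exact method. The primary FAS conclusion is unaffected. This is a cheap improvement to a secondary analysis set.

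**What to change.** Reword the first PP exclusion so that it removes subjects without on-treatment HIV-1 RNA in the Week 48 window, except those whom the snapshot algorithm classifies as HIV-1 RNA ≥ 50 copies/mL by either b)1) or b)2). This is one sentence in the protocol and in the Week 48 analysis plan. It needs no new data, visits or subjects.

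If the Week 48 PP analysis has already been run, leave the defined set alone. Report the b)2) count by arm and rerun PP with these women kept, labelled as a sensitivity analysis.

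The cost is that PP failure rates may look slightly less favourable.

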#### 8.2.1.3. Safety

The primary analysis set for safety analyses is defined as safety analysis set, which will include all subjects who (1) are randomized into the study and (2) have received at least 1 dose of study drug. All the data collected up to 30 days after subjects permanently discontinue their study drug will be included in the safety summaries, unless specified otherwise. Subjects will be grouped according to the treatment they actually received.

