### 6.4. Treatment Assessments (Weeks 4-48)

The following evaluations are to be completed at the end of Weeks 4, 8, 12, 24, 36, and 48 unless otherwise specified.

Study visits are to be completed within  $\pm$  2 days of the protocol-specified visit date based on the Day 1 visit through Week 12 and completed within  $\pm$  6 days at Week 24 and Week 36, unless otherwise specified. The visit window at Week 48 will be  $\pm$  6 weeks of the protocol-specified visit date, and these clinical visit windows coincide with the Week 48 statistical analysis window for HIV-1 RNA.

Regularly scheduled evaluations will be made on all subjects whether or not they continue to receive study drug.

- Review of AEs and changes in concomitant medications
- Complete physical examination (**Weeks 24 and 48**) (urogenital/anorectal exams will be performed at the discretion of the Investigator) or symptom-directed physical examination as needed
- Vital signs measurement (blood pressure, pulse, respiration rate, and temperature), including weight
- 12-lead ECG performed supine (**Weeks 24 and 48**)
- Urine collection for the following laboratory procedures:
  - Urinalysis
  - Urine albumin, urine creatinine, urine protein, retinol binding protein and beta-2 microglobulin (**Weeks 24 and 48**)
  - Urine pregnancy test (females of childbearing potential only); positive urine pregnancy tests will be confirmed with a serum test. If the test is positive, subjects on GS-9883/F/TAF will be discontinued.
  - Urine storage sample for possible additional clinical testing

- Blood sample collection for the following laboratory analyses:
  - Chemistry profile: alkaline phosphatase, AST, ALT, GGT, total bilirubin, direct and indirect bilirubin, total protein, albumin, bicarbonate, BUN, calcium, chloride, creatinine, glucose, phosphorus, magnesium, potassium, sodium, uric acid, and amylase (reflex lipase testing is performed in subjects with total amylase  $> 1.5 \times$  ULN). At Weeks 12, 24 and 48, analyses of glucose will be done as part of the fasting metabolic assessments and not as part of the chemistry profile. At Weeks 24 and 48, TSH will also be analyzed.

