### **7.3.1. Adverse Events**

Following initiation of study medication, collect all AEs, regardless of cause or relationship, until 30 days after last administration of study IMP must be reported to the eCRF database as instructed.

All AEs should be followed up until resolution or until the adverse event is stable, if possible. Gilead Sciences may request that certain AEs be followed beyond the protocol defined follow up period.

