### **8.6.2. Adverse Events**

Clinical and laboratory adverse events will be coded using the Medical Dictionary for Regulatory Activities (MedDRA). System Organ Class (SOC), High-Level Group Term (HLGT), High-Level Term (HLT), Preferred Term (PT), and Lower-Level Term (LLT) will be attached to the clinical database.

Events will be summarized on the basis of the date of onset for the event. A treatment-emergent adverse event will be defined as any adverse event with onset date on or after the study drug start date and no later than 30 days after the study drug stop date; or any adverse event leading to study drug discontinuation.

Summaries (number and percentage of subjects) of treatment-emergent adverse events (by SOC, HLT [if applicable], and PT) will be provided by treatment. Additional summaries will include summaries for adverse events by grade, Investigator's assessment of relationship to study drug, and effect on study drug dosing.

On an ongoing basis adverse events will be reviewed for events that might meet the definition of Stage 3 Opportunistic Illnesses in HIV are indicative of an AIDS-Defining Diagnoses. The Gilead medical personnel will review the possible Stage 3 events and approve the events that meet the definition. Those events that do meet the Stage 3 Opportunistic Illnesses definition of an AIDS-Defining Diagnosis will be listed.

A listing of Stage 3 Opportunistic Illnesses in HIV can be found in [Appendix 5](#).

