### **4) Procedures to be Followed in the Event of Pregnancy**

Subjects will be instructed to notify the investigator if they become pregnant at any time during the study, or if they become pregnant within 30 days of last study drug dose. Subjects who become pregnant or who suspect that they are pregnant during the study must report the information to the investigator immediately. The investigator will counsel the subject regarding pregnancy management options. Counseling will be provided regarding alternative anti-HIV treatment. Information on the risks and benefits of antiretroviral therapies will be discussed, including the risk of ongoing fetal exposure to the study drug versus the new alternative therapy and the risk of discontinuing maternal therapy.

If the subject is on GS-9883/F/TAF, they must discontinue study drug immediately. Subjects may be allowed to continue on study drug if they are taking E/C/F/TAF, E/C/F/TDF or ATV+RTV+FTC/TDF and an additional informed consent will be required.

If the subject elects to discontinue study drugs but remain in the study, a new ARV regimen will be constructed at the Investigator's discretion.

The Investigator should counsel the subject on the need to inform the study site of the outcome of the pregnancy. Information collected will include gestational dating, ultrasound report, records of maternal, fetal complications and pregnancy outcome.

Instructions for reporting pregnancy and pregnancy outcome are outlined in Section [7.6](#).

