7.6. Other Safety Measures

A data listing will be provided for subjects experiencing pregnancy during the study. Physical examination was not collected in the eCRF. Therefore, it will not be included in the analysis.

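### After a pregnancy, the safety-summary window can be much shorter on GS-9883/F/TAF than on the baseline regimen, so a late pregnancy-related SAE may be tabulated in one arm and only listed in the other

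*Protocol*

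**What the plan says.** **Summary window.** Protocol 8.2.1.3: "All the data collected up to 30 days after subjects permanently discontinue their study drug will be included in the safety summaries", with room for exceptions specified elsewhere. Section 8.6 repeats the limit and assigns data after last dose plus 30 days to listings. Section 8.6.2 defines a treatment-emergent event as one with "onset date on or after the study drug start date and no later than 30 days after the study drug stop date", or one leading to discontinuation of study drug. None of the three sections mentions pregnancy.

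**Pregnancy rule by arm.** Protocol 6.4, on a confirmed pregnancy test: "If the test is positive, subjects on GS-9883/F/TAF will be discontinued". Appendix 6, item 4: "If the subject is on GS-9883/F/TAF, they must discontinue study drug immediately". For the comparator the same item says "Subjects may be allowed to continue on study drug if they are taking E/C/F/TAF, E/C/F/TDF or" the atazanavir-based regimen, with an additional informed consent. Section 6.7 lists pregnancy, without distinguishing arms, among the reasons for which study medication may be discontinued.

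**Collection and reporting.** Section 7.6.2.1: "A spontaneous abortion is always considered to be an SAE". It also makes adverse pregnancy-outcome SAEs reportable after the study and asks for the outcome of each pregnancy. Section 7.3.2 requires SAE reporting from consent throughout the study. For adverse events in general, 7.3.1 says "collect all AEs, regardless of cause or relationship, until 30 days after last administration of study IMP". Section 6.4, however, schedules evaluations, including adverse-event review, whether or not a woman is still on drug, and 6.6.1 asks women who stop to attend through Week 48.

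**SAP.** Section 7.6: "A data listing will be provided for subjects experiencing pregnancy during the study". Sections 2.3 and 3 limit this SAP to an analysis of B/F/TAF alone; the SBR data were analysed at Week 48.

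**The concern.** The end of the summary window is tied to the last dose, and on pregnancy the protocol makes the last dose depend on the arm. Two women with the same pregnancy, detected on the same study day and lost on the same later day, can be treated differently: one event enters the SAE table and the other appears only in a listing. Where the arms differ, the omission is from the GS-9883/F/TAF column.

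The trial enrols only women. Section 1.10 gives adequate safety data in women as a reason for doing it, and Appendix 6 acknowledges that pregnancy data on the test product are limited or lacking. The secondary objective is safety and tolerability through Week 48, a horizon within which SAEs are collected in both arms. With few pregnancies, one or two events could change how the comparative SAE table reads. The virologic endpoints are not involved.

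**Working it through.** **The plan's own figures.** The documents give no figure for pregnancies or pregnancy-related SAEs. The one checkable figure, power, reproduces: Φ(0.04/√(2 × 0.02 × 0.98/235) − 1.96) = 0.872, against at least 87% stated. Nothing below affects it.

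**Step 1: can the discontinuation clause bring the event back?** Section 8.6.2 also counts events leading to discontinuation. Section 7.6.2.1 says the pregnancy itself is not an adverse event, and a loss or complication arising weeks after the stop did not cause it. The clause does not apply.

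**Step 2: length of the window after detection.** Inputs: the 30-day limit (8.2.1.3), 30/7 = 4.3 weeks; stop at detection in the test arm (Appendix 6); SBR treatment ending no later than Week 48.

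- Test arm: 4.3 weeks.
- SBR, continuing c weeks after detection: c + 4.3 weeks.
- Share of SBR summary time with no test-arm counterpart: c/(c + 4.3).

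If the SBR woman also stops at detection, c = 0 and the share is 0%. If she continues to Week 48 after detection at Week w, c = 48 − w, the maximum:

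| Detected at | Test-arm window (weeks) | Longest SBR window (weeks) | Largest share without counterpart |
|---|---|---|---|
| Week 12 | 4.3 | 36 + 4.3 = 40.3 | 36/40.3 = 89% |
| Week 24 | 4.3 | 24 + 4.3 = 28.3 | 24/28.3 = 85% |
| Week 36 | 4.3 | 12 + 4.3 = 16.3 | 12/16.3 = 74% |

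**Step 3: allow for delivery.** Some of the longest SBR windows outlast the pregnancy. Assume (not in the documents) a 40-week gestation, detection spread evenly over Weeks 0 to 48, and an SBR woman on drug until Week 48 or delivery. With detection at gestational week g and study week t, her window is the smaller of 40 − g and 48 − t + 4.3. Averaged over t, this is 25.2, 24.0, 22.1 and 20.0 weeks for g = 5, 8, 12 and 16. The test-arm window of 4.3 weeks is about 17% to 21% of these. They remain upper-end cases, because they assume she continues.

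**Step 4: how many events?** Assumed inputs only: 2 to 10 test-arm pregnancies, 5% to 30% of them with an SAE after the 30-day window. That gives 2 × 0.05 = 0.1 to 10 × 0.30 = 3.0 women, or 0.04% to 1.3% of 235.

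**Step 5: what is lost?** For SAEs, only their place in the summary tables: 7.3.2 and 7.6.2.1 keep them reportable and 8.6 keeps them listed. For non-serious events the documents conflict: 7.3.1 ends collection 30 days after the last dose, while 6.4 reviews adverse events at scheduled visits on or off drug.

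**The case against.** Last dose plus 30 days is a standard convention that ties harms to exposure. A woman who stops but remains in the study starts another antiretroviral regimen, so her later events are confounded by it. Contraception and repeated testing are required, so pregnancies should be few. Continuing on SBR is optional and needs extra consent; if the SBR woman stops, the windows are equal. Events within 30 days of the stop are tabulated in both arms. Section 8.2.1.3 allows exceptions, and the plan for the Week 48 comparison, where one might be written, was not supplied.

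Most of this limits the size. It does not remove the mechanism: no supplied section makes a pregnancy exception, and an exposure-based table can be kept with a second table beside it.

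Three stronger readings are tempting. A reader might infer that pregnancy-related SAEs go uncollected in the test arm; 7.3.2 and 7.6.2.1 say otherwise. A reader might infer that non-serious events after day 30 are never recorded for her; 6.4 and 6.6.1 point the other way, so the text is inconsistent and does not settle it. And a reader might take the pregnancy listing in SAP 7.6 as the only pregnancy output of the randomised comparison; that SAP covers B/F/TAF alone and cannot show what the Week 48 analysis contained.

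**Conclusion.** The point holds as a difference between arms in the treatment-emergent and safety-summary window after pregnancy. Where an SBR woman continues on drug, a late pregnancy-related SAE would be counted for her and only listed for her GS-9883/F/TAF counterpart, which favours the test arm in the tables.

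The unmatched share of SBR summary time is 0% to 89%, 85% or 74% for detection at Week 12, 24 or 36. The upper figures require continuation to Week 48 and must not be read as typical or as a proportion of events missed. The number of events is unknown and probably small. The conclusion assumes that the Week 48 comparison followed the protocol rule without an exception, which the documents neither confirm nor exclude. It warrants an inexpensive improvement to reporting; it does not challenge the trial's primary conclusion.

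**What to change.** In Protocol 8.2.1.3 and 8.6.2, and in the plan for the Week 48 comparison, add one supplementary table beside the on-treatment SAE table. Suggested text: *Pregnancy outcomes and pregnancy-related SAEs will be summarised by randomised group for every pregnancy conceived during randomised treatment or within 30 days of its last dose, regardless of when study drug was stopped. Events occurring after the start of another antiretroviral regimen will be footnoted.* SAP 2.2 reports that the Week 48 analysis has been run, so first check whether it already holds such a table.

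The on-treatment tables stay as they are. Two sets of passages must be reconciled: 7.3.1 with 6.4 on adverse-event collection after stopping; and 6.4, 6.7 and Appendix 6 on whether pregnancy discontinuation is mandatory or permitted, and in which arm. No view is taken on which clinical rule is right, and the table does not require changing the stop and continue rules.

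Costs: one small table, and reconciliation of the pregnancy outcome forms held by the sponsor's drug-safety group with the clinical database, since the documents do not say that those outcomes enter it. Confounding by the later regimen remains; the footnote discloses it without removing it. Sample size, power and the primary analysis are unaffected.
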